19.7 Missing Date Information for Adverse Events

For AEs, incomplete (i.e., partially missing) start dates will be imputed and will follow the same rules as in Section 19.6.1. Incomplete stop dates will not be imputed.

19.8 Missing Severity Assessment for Adverse Events

If severity is missing for an AE starting prior to the date of the first dose of double-blind investigational product, then a severity of "Mild" will be assigned. If the severity is missing for an AE starting on or after the date of the first dose of double-blind investigational product, then a severity of "Severe" will be assigned. The imputed values for severity assessment will be used for incidence summaries, while the actual values will be used in data listings.

19.9 Missing Relationship to Investigational Product for Adverse Events

If the relationship to investigational product is missing for an AE starting on or after the date of the first dose of double-blind investigational product, a causality of "Related" will be assigned. The imputed values for relationship to double-blind investigational product will be used for incidence summaries, while the actual values will be presented in data listings.

19.10 Character Values of Clinical Laboratory Variables

The actual values of clinical laboratory variables as reported in the database will be presented in data listings. No coded values (e.g., when a character string is reported for a numerical variable) are necessary.

21. TABLE OF CONTENTS FOR FIGURES, TABLES, AND LISTINGS

Table of contents for figures, tables and listings will be documented separately.

22. APPENDICES

22.1 Appendix 1 Algorithms for Sample Size Re-estimation

Based on the rationale that the total variance is similar to the within group variance as long as the treatment effect is not too large, a pooled common variance can be estimated by using blinded cumulative primary efficacy data that are collected during the study, up to the time of sample size re-estimation. The pooled common variance can be used along with the pre-specified treatment difference to re-estimate the sample size. Below are steps in details:

• Ignoring treatment difference and applying the formula below to estimate the pooled sample variance, which is an unbiased estimate of the variance.

$$S_{pooled}^2 = \frac{1}{n_1 - 1} \sum_{i,j} (X_{ij} - \bar{X})^2$$
,

where n_1 is total number of subjects who either completed or discontinued from the study at the time point of the sample size re-estimation. i=1,2; $j=1,\dots,n_{1i}$ and $n_1=n_{11}+n_{12}$.

• Let Δ^* be the alternative hypothesis of treatment mean difference that is pre-specified as 11.9, for which the study is powered. Hence, a common variance that can be used for the sample size re-estimation is:

$$S_{final}^2 = S_{pooled}^2 - \frac{n_1}{4(n_1 - 1)} \Delta^{*2}$$

• Applying S_{final}^2 and the assumed true mean treatment effect difference together, an updated effect size can be calculated. Using the effect size, the sample size can be re-estimated (Friede et al, 2006).

Furthermore, the blinded sample size re-estimation only allow upwards adjustments of the initially (at the study design stage) planned sample size, and using the pooled common variance estimated above to do a blinded sample size-estimation does not inflate the Type I error rate (Friede et al., 2006).

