The safety data on TEAEs will also be descriptively summarized by treatment within each age group (6-8 years vs. 9-12 years), sex, race, and ethnicity subgroups.

Sample Size Calculation and Power Considerations

Approximately 60 subjects will be randomized in a 1:1 ratio to SHP465 6.25 mg and placebo to achieve 52 completers for the study (26 in each treatment group) and 85% power for the primary efficacy analysis at the 2-sided 0.05 significance level.

07 September 2017

The sample size planned is estimated based on the primary comparison between SHP465 6.25 mg and placebo on the primary efficacy endpoint change from baseline in ADHD-RS-5 total score at Visit 6 (Week 4). Assumptions for the calculation include the true mean difference of 11.9 with the common standard deviation (SD) of 14 for an effect size of 0.85, and a dropout rate of 15%.

The effect size of 0.85 is low compared with that observed in recently completed study (SHP465-305) of children and adolescents aged 6-17 years with ADHD treated with SHP465. The SHP465-305 study yielded an effect size of 0.93 in children aged 6-12 years (N=101 subjects).

Planned Interim Analysis

A blinded interim analysis at the late stage of the trial (when approximately 75% of all randomized subjects have either completed or discontinued from the study) will be performed to reassess the sample size in case of an underestimated variability postulated at the design stage.

Using the cumulative real data, a blinded, pooled analysis of both treatment groups for estimating variability will be conducted on the change from baseline in ADHD-RS-5 total score at Visit 6 (Week 4). If the re-estimated pooled standard deviation is larger than the 14 postulated at the design stage, the final total number of subjects to be enrolled will be calculated using the re-estimated pooled standard deviation together with the assumed treatment difference of 11.9 (Friede et al, 2006). If the re-estimated pooled standard deviation is smaller than 14, the sample size will not be adjusted.

SHP465-309

07 September 2017

STUDY SCHEDULE(S)

Table 1: Schedule of Assessments

	Screening/Washout ^a		Baseline		Follow-up				
Visit Number ^b	1	Phone call	2	3	4	5	6/ET ^c	Phone ca	
Study Week	-5 to -1	-1	0	1	2	3	4	5	
Study Day ^b	-32 to -3	-7	0	7	14	21	28	35	
Informed consent/assent	✓								
Inclusion/exclusion criteria	✓	√d	√d						
Subject demography	√								
MINI-Kid	✓								

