2.5 Determination of Sample Size

The primary efficacy endpoint is defined as the change from baseline in the Attention-deficit/Hyperactivity Disorder Rating Scale Version 5 (ADHD-RS-5) total score at Visit 6 (Week 4). The baseline ADHD-RS-5 total score is the last value obtained prior to taking the first dose of investigational product, usually at Visit 2.

The null hypothesis is that there is no difference in mean change from baseline at Visit 6 (Week 4) in ADHD-RS-5 total score between SHP465 6.25 mg and placebo, and the alternate hypothesis is that there is a difference in mean change from baseline at Visit 6 (Week 4) in ADHD-RS-5 total score between SHP465 6.25 mg and placebo.

The sample size was estimated for the primary comparison of SHP465 at 6.25 mg with placebo by using nQuery Advisor 7.0. To detect an assumed difference of 11.9 for the change from baseline in the ADHD-RS-5 total score between the SHP465 at 6.25 mg treatment group and the placebo group with the assumed common standard deviation (SD) of 14, 26 completers per group are needed to provide 85% power for a 2-sided t-test with α level of 0.05. This yields a total of 52 subjects (26 on active treatment and 26 on placebo). Taking into account an expected post-randomization dropout rate of 15%, the randomization target is set at 60 subjects in total.

The assumptions of a treatment difference of 11.9 and a standard deviation of 14.0 corresponds to an effect size of 0.85 which is low compared with that in recently completed study (SHP465-305) of children and adolescents aged 6-17 years with ADHD treated with SHP465. The SHP465-305 study yielded an effect size of 0.93 in children aged 6-12 years (101 subjects).

A blinded interim analysis at the late stage of the trial (when approximately 75% of all randomized patients have either completed or discontinued from the study) is needed for a possible sample size increase in case of an underestimated variability postulated at the design stage (see Section 15).

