2.5.1 Sample Size Update

Following the SAP Section 2.5 and the protocol Section 9.6, a blinded interim analysis for sample size re-estimation was performed based on 47 randomized subjects as of 19 March 2018 (the interim cohort), among which 45 were in the FAS and 43 completed the study. Data of the interim cohort were extracted on 27 April 2018, after the collection of all their primary efficacy data.

The pooled standard deviation for Visit 6 (Week 4) used for sample size re-estimation was calculated using a pooled common variance that was estimated by using blinded cumulative primary efficacy data in the interim cohort. Then the final pooled standard deviation was

calculated as stated in Section 15 and Appendix 1. The interim analysis results showed a reestimated pooled standard deviation of 13.29 which is less than 14 and therefore an increase to the sample size was not required.

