15. INTERIM ANALYSIS

In order to maintain sufficient study power to detect a clinically meaningful treatment effect for the primary efficacy endpoint, a blinded interim analysis at the late stage of the trial (when approximately 75% of all randomized subjects have either completed or discontinued from the study) will be performed to reassess the sample size in case of an underestimated variability postulated at the design stage.

Using the cumulative real data, a blinded, pooled analysis of both treatment groups for estimating variability will be conducted. If the re-estimated pooled standard deviation is larger than the 14 postulated at the design stage, the final total number of subjects to be enrolled will be calculated using the re-estimated pooled standard deviation together with the assumed treatment difference of 11.9 (Friede et al, 2006). If the re-estimated pooled standard deviation is smaller than 14, the sample size will not be adjusted. Using the pooled common variance estimated to do a blinded sample size re-estimation does not inflate the Type I error. The details for estimating the pooled SD are included in Appendix 1.

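### Does the interim SD of 13.29 rest on a divisor that counts subjects with no Week 4 value, and was the sample size therefore wrongly left unchanged?

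*SAP*

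**What the plan says.** The Planned Interim Analysis paragraph of the protocol synopsis says that the blinded variability estimate "will be conducted on the change from baseline in ADHD-RS-5 total score at Visit 6 (Week 4)". SAP Section 15 sets the rule: "If the re-estimated pooled standard deviation is larger than the 14 postulated at the design stage", the total is recalculated from the new SD and the assumed difference of 11.9; otherwise nothing changes.

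SAP Appendix 1 gives the estimator in two steps. The first is the sample variance of the blinded data about the overall mean, with divisor n1 − 1, introduced as "applying the formula below to estimate the pooled sample variance, which is an unbiased estimate of the variance". There n1 is the "total number of subjects who either completed or discontinued from the study at the time point of the sample size re-estimation", and the same sentence makes n1 the sum of the two arm counts over which the index j runs. The second step subtracts n1Δ*²/(4(n1 − 1)), with Δ* fixed at 11.9, to give S²_final. X_ij is not defined, and nothing is said about subjects without a Week 4 value.

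SAP Section 2.5.1 reports the completed interim: 47 randomized subjects, "among which 45 were in the FAS and 43 completed the study". It then states: "The interim analysis results showed a reestimated pooled standard deviation of 13.29 which is less than 14". No increase was made. The design target in SAP Section 2.5 is that "26 completers per group are needed to provide 85% power for a 2-sided t-test with α level of 0.05".

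**The concern.** A subject who discontinues in Week 1 or 2 normally has no Week 4 change. Read literally, n1 counts that subject in the divisor although he or she adds nothing to the sum of squares. With m observed values, the pooled variance then shrinks by the factor (m − 1)/(n1 − 1). The interim look exists to protect power if the true SD exceeds 14, so an estimate biased low would weaken that safeguard.

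The reported 13.29 also lies close to the threshold, and the SAP states neither the divisor nor the number of values behind it. A modest upward correction could carry it past 14.

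Two smaller points add to the unease. The pooled variance is called unbiased just before a correction is subtracted from it. And S_final equals the within-arm SD only if the true effect is 11.9.

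**Working it through.** **Inputs.** Difference 11.9, SD 14, two-sided 0.05, 85% power, 26 completers per arm, 15% dropout (SAP Section 2.5); trigger 14 (SAP Section 15); 47 randomized, 45 FAS, 43 completers, SD 13.29 (SAP Section 2.5.1); formulas from SAP Appendix 1. Section 2.5.1 says the final pooled SD was obtained as in Section 15 and Appendix 1, so 13.29 is read as S_final.

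**Design figure.** A two-sample t-test (noncentral t) with difference 11.9 and SD 14 has 85.2% power at 26 per arm and 83.8% at 25. The plan's 26 reproduces.

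**Undoing the reported SD, taking n1 = 47.**
- S²_final = 13.29² = 176.62
- Correction = 47/(4 × 46) × 11.9² = 36.17
- S²_pooled = 176.62 + 36.17 = 212.80 with unrounded inputs (SD 14.59)
- Sum of squares = 46 × 212.80 = 9788.6

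**Recomputing with m values in both terms:** S² = 9788.6/(m − 1) − m × 11.9²/(4(m − 1)).

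| Values m | First term | Correction | SD | Needed per arm | Power at 26 per arm |
|---|---|---|---|---|---|
| 43 | 233.06 | 36.25 | 14.03 | 26 | 85.1% |
| 44 | 227.64 | 36.23 | 13.84 | 26 | 86.0% |
| 45 | 222.47 | 36.21 | 13.65 | 25 | 86.9% |

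If the divisor was instead based on the 45 FAS subjects with 43 values, the same steps give 13.66 and 86.8% power. If sum and divisor already matched, 13.29 stands.

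**Which n matters.** Only the divisor of the sum of squares does. Using 47 instead of 43 in the correction alone changes it from 36.25 to 36.17, which moves the SD by about 0.07/(2 × 13.29), or 0.003.

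**Range of m.** The two subjects outside the FAS cannot contribute, because the FAS requires a post-dose score. The two FAS non-completers might: early terminators undergo the Visit 6 assessments, and SAP Section 19.3 assigns those to the next nominal visit, which is Visit 6 for someone who left after Visit 5. So m lies between 43 and 45 if every completer has a Week 4 score. SAP Section 6 defines completers as those who completed Visit 6, and Section 2.5.1 says the data were extracted after all primary efficacy data had been collected. The margin is thin: with m = 42 and n1 = 47 the SD would be 14.23, the need 27 per arm, and power at 26 per arm 84.1%.

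**Effect on the rule.** At 14.03 the recalculation is triggered and returns 26 per arm, or 52 completers. The plan turned 52 into 60 (52 × 1.15 = 59.8), so its own route leads back to 60.

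**Size of the bias in general**, if the mismatch occurs, the effect is 11.9 and the arms are balanced: expected S²_final = [(m − 1)σ² − (n1 − m) × 11.9²/4]/(n1 − 1).
- m = 43, n1 = 47, σ = 14: (8232 − 141.61)/46 = 175.88, SD 13.26. The estimate reaches 14 on average at σ of about 14.8, where 26 per arm have 81.3% power.
- m = 38, n1 = 45 (15% dropout at the planned look), σ = 14: (7252 − 247.82)/44 = 159.19, SD 12.6. The effective trigger is about 15.5, with 77.6% power at 26 per arm.

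**The case for a change.** The strongest case for a change is that the formula cannot be evaluated as written: it calls for n1 values, and some of them do not exist. Taken at its word, the definition of n1 leads to the biased version. At the planned dropout rate that would be material, with 77.6% power at the effective trigger, where 32 per arm would be needed for 85%. The only published interim result cannot be reproduced from the SAP, and one reading puts it on the other side of the only threshold. The remedy would be cheap.

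It stands that X_ij is undefined, that the n behind 13.29 is not reported, and that the bias is real under that reading. It does not follow that the mismatch happened. Sum and divisor share one index set in Appendix 1, and a standard variance routine drops missing values from both. The 38-of-45 case did not arise: the interim had 43 completers among 47, so 4/47 = 8.5% did not complete.

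The side points carry little. The bullet that says unbiased opens by setting the treatment difference aside; under that condition the word is right, and the next bullet makes the adjustment. The dependence on 11.9 is stated openly and belongs to the chosen method. If 13.29 were S_pooled rather than S_final, the SD corrected for 43 values would be 12.5, further below 14.

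**Conclusion.** No change is called for. Appendix 1 leaves out a detail that an analyst would fill sensibly by computing the variance over subjects with a Week 4 change. The documents do not show that anything else was done. Under the least favourable reading the SD rises from 13.29 to 14.03, and the requirement stays at 26 completers per arm with 85.1% power. Under the other readings it is 26 per arm or fewer. The interim is complete, and correcting the definition would alter no sample size, analysis or conclusion; a note of the n behind 13.29 would be a courtesy to the reader.

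This rests on four assumptions: 13.29 is S_final; all 43 completers supplied a Week 4 score; the true effect is 11.9, as the method presumes; and the arms in the interim cohort were about equal in size.

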22.2 Appendix 2 Sample SAS Codes

Mixed Model Repeated Measures (MMRM)

```
Proc mixed /* select derived data set */;
Class trt subjid visit agegp;
Model chg = trt visit agegp trt*visit base base*visit / ddfm=kr;
Repeated visit / subject=subjid type=UN;
/* LSMean, Estimate, and/or LSMestimate statement(s) */
/* Data output or object delivery statement(s) */
Run;
```

Mixed Model Repeated Measures (MMRM) for subgroup analysis

```
Proc mixed /* select derived data set */; Class trt
subjid visit;
Model chg = trt visit trt*visit base base*visit / ddfm=kr; Repeated visit /
subject=subjid type=UN;
by subgroup;
/* LSMean, Estimate, and/or LSMestimate statement(s) */
/* Data output or object delivery statement(s) */
Run;
```

Analysis of Covariance (ANCOVA)

```
Proc glm /* select derived data set */;
Class trt;
Model chg = trt agegp base/alpha=.05;
Lsmeans trt/stderr pdiff;
/* Data output or object delivery statement(s) */
Run;
```

Missing Not at Random (MMNAR) Sensitivity Analysis

Model 1: Placebo Multiple Imputation

```
* Step 1;
proc mi data=unimputed out=discard nimpute=200 seed=309 noprint;
    where treatment=1; * where 1 stands for placebo;
    var baseline chy1-chy4;
    mcmc outest=posteriors; * here we pick up the PLA posteriors;
run;

* 100 posteriors for the placebo, rest for SHP465 6.25 mg;
data posteriors(type=est);
    set posteriors;
```

```
if 1<=_imputation_<=100 then do; * assign placebo posteriors;
              treatment=1;
         end;
        if 100<_imputation_<=200 then do; * assign posteriors to SHP465 6.25 mg;
              treatment=2;
              _imputation_=_imputation_-100;
        end;
 run;
 proc sort data=unimputed;
    by treatment;
 run;
 proc mi data=unimputed out=imputed;
    by treatment;
    var baseline chy1-chy4;
    mcmc inest=posteriors; * here we use the placebo posteriors;
 run;
 * Step 2;
data endpoint;
    set imputed;
    endpoint=chy4;
run;
 proc sort data=endpoint;
    by _imputation_;
 run;
 proc glm data=endpoint;
    by _imputation_;
    class treatment agegp;
    model endpoint = baseline treatment agegp / solution;
    Ismeans treatment;
    estimate 'SHP465 6.25 mg vs placebo' treatment -1 1;
    ods output estimates=est;
 run;
 * Step 3;
 proc sort data=est;
    by label_imputation_;
 run;
 proc mianalyze data=est;
    by label;
    modeleffects estimate;
    stderr stderr;
 run;
```

Protocol SHP465-309

Model 1.

Model 2: Multiple Imputations with Penalties Applied to Dropouts

* Note: dataset "unimputed" has one row per subject, repeated measures are structured in columns; * Step 1; data unimputed; set unimputed; missing=(Chy4 =.); run; proc sort data=unimputed; by treatment; run; proc mi data=unimputed out=imputed nimpute=&nimpute seed=309 noprint; by treatment; var baseline chy1-chy4; run; %let SD=10; * This will be replaced by the estimated SD[chy5] from the MMRM co-variance matrix R (use R or RCORR option in REPEATED statement under PROC MIXED); %let penalty=0.25*&SD; * Repeat this step for various values (0.25, 0.5, 0.75 and 1) as per SAP; data imputed; set imputed; if missing then chy4=chy4+ &penalty; * + or -, depending on the measure; run; * Step 2 (analysis of completed data sets) and Step 3 (inference) are the same as Steps 2 and 3 respectively for
